3.5	Ocular Symptoms	Subjects will respond to a verbal open-ended symptoms questionnaire
3.6	Subjective Acceptance	Record whether the subjects distance and near vision with the lenses is acceptable.
3.7	Distance and Near Entrance Visual Acuity	
Measure the distance and near visual acuity OD, OS and OU. Record the results.
 
For near measures use the ETDRS 2000 Series Chart 1 or 2. The acuity will be recorded to the nearest letter OD, OS and OU.

3.8	Visual Performance Distance (3M) Intermediate (64 cm) Near (40 cm)	
Visual performance will be recorded OD, OS, and OU for the following:
 
Distance, Bright Illuminance
 
High and Low Contrast ETDRS Charts 3M- HC#1, HC#2, HC#3 and LC#1, LC#2, LC#3
 
Near, Bright Illuminance

		
Reduced Guillot-Polking Charts Intermediate (64 cm) High Contrast and Low Contrast Near (40 cm) High Contrast and Low Contrast
 
Distance, Dim Illuminance (with Distance goggles) High Contrast ETDRS Charts 3M-HC#4, HC#5, HC#6
 
Near, Dim Illuminance (with Near goggles) Reduced Guillot-Polking charts High Contrast Intermediate (64 cm) and Near (40 cm).
 
Note:
 
 • The room illuminance must be between 7.3 and 7.9 EV (394-597 lux). • Distance, HC-1 Chart luminance Acceptable Range 10.5-10.7 EV (181-208 cd/m²). • Guillot-Polking, Near Chart Luminance Acceptable Range 10.8-11.1 EV (223-274 cd/m²). • Do not use the Mesopic filter for Dim luminance (Dim luminance will be simulated by using the goggles) 	
3.9	Binocular Distance Over-refraction and Distance Visual Acuity	
Perform a binocular over-refraction and record the OD and OS results and distance visual acuity.
 
Note: No lens changes are allowed based on the over-refraction.
	Appendix D
3.10	Lens Fit Assessment:	
Evaluate and grade lens centration, primary gaze movement, upgaze movement and tightness (push-up test).
 
 • The subject should not proceed to wear the lenses if any of the following is observed: • presence of limbal exposure (appearance of clear cornea) in any gaze • presence of edge lift • presence of unacceptable movement (excessive or insufficient) in all three movement categories (primary gaze, upgaze, and push-up). 	

		
If either lens is deemed unacceptable, the subject will be discontinued from the study. Remove the lenses, perform a slit-lamp evaluation, and complete the Final Evaluation form.
	
3.11	Lens Removal	
Have the subject remove the study lenses and store in saline in a labeled glass vial.
 
Note: Lenses do not need to be stored in a refrigerator.
	
3.12	Biomicroscopy	
Perform biomicroscopy OD and OS. Slit Lamp Classification Scales will be used to grade the findings.
 
For the conjunctival redness [REDACTED] 0.5 unit increments will be used in the grading.
 
Corneal Staining Assessment [REDACTED] will be graded in 1.0 increments.
 
If the clearance of the fluorescein needs to be expedited, preservative-free rewetting drops or saline may be instilled.
	[REDACTED] [REDACTED] [REDACTED]
3.13	Distance and Near Exit Visual Acuity	
Distance and near Snellen visual acuity will be measured for each eye with the subject's habitual correction in place.
 
For near measures use the ETDRS 2000 Series Chart 1 or 2. The acuity will be recorded to the nearest letter OD, OS and OU.
	[REDACTED]
3.14	Schedule Follow-up	
The subject will be scheduled to return for their next appointment in 7 ± 3 days.
 
Note: Subject may wear their habitual spectacles or contact lenses during the washout period.
	

VISIT 4

The subjects may present to Visit 4 wearing their habitual spectacles or contact lenses.

Visit 4: Baseline Treatment 2		
Step	Procedure	Details
4.1	Adverse Events and Concomitant Medications Review	Review the subject's concomitant medications and record any changes from the previous study visit. Record any adverse events or medical history changes from the previous study visit.
4.2	Subject Reported Ocular Symptoms	Subjects will respond to a verbal open-ended symptoms questionnaire.
4.3	Distance and Near Entrance Visual Acuity	Distance and near Snellen visual acuity will be measured for each eye with the subject's habitual correction in place. For near measures use the ETDRS 2000 Series Chart 1 or 2. The acuity will be recorded to the nearest letter OD, OS and OU.
4.4	Lens Removal (if applicable)	Have the subject remove their habitual lenses and store in an approved storage solution.
4.5	Biomicroscopy	FDA Slit Lamp Classification Scale will be used to grade the findings and determine eligibility. For the conjunctival redness [REDACTED] 0.5 unit increments will be used in the grading. Corneal Staining Assessment [REDACTED] will be graded in 1.0 increments. If the clearance of the fluorescein needs to be expedited, preservative-free rewetting drops or saline may be instilled.
4.6	Continuance	Determine whether the subject is eligible to continue in the study based on the examination findings.

Visit 4: Treatment 2 Lens Fitting		
Step	Procedure	Details
4.7	Lens Selection	Select the lens pair based on the randomization scheme and select the power that was dispensed at Visit 2 for each eye. Record the Test lens parameters (power and lot number).
4.8	Lens Insertion	Subjects will insert the lenses themselves. If

		
the lens is uncomfortable, inspect for damage and remove, reinsert or replace as necessary.
 
Damaged lenses will be stored in labeled vial with sterile saline, and clearly differentiated from the other worn lenses that will be shipped back to the Sponsor. Complete the Quality Product Complaint form.
	
4.9	Lens Settling	Allow the study lenses to settle for a minimum of 10 minutes.	
4.10	Distance and Near Entrance Visual Acuity	
Measure the distance and near visual acuity OD, OS and OU. Record the results.
 
For near measures use the ETDRS 2000 Series Chart 1 or 2. The acuity will be recorded to the nearest letter OD, OS and OU.
	[REDACTED]
4.11	Determine Visual Satisfaction	
Determine if the subject's vision is acceptable with the lenses. Allow the subject to look down a hallway or out of a window for distance vision assessments, and for them to read a book, magazine or similar for near vision.
 
Note: If the subject's vision is unacceptable the subject will be discontinued. Complete the final evaluation.
	
4.12	Distance Over-Refraction and Distance Visual Acuity	Perform a distance over-refraction OD and OS using loose lenses outside of the phoropter under ambient room illumination. The distance over-refraction may also be refined under binocular conditions. Record the results. The results of the distance over-refraction may also be checked for the impact on near vision under monocular and/or binocular conditions.	
4.13	Subjective Lens Fit Assessment	
Evaluate overall lens fit acceptance (acceptable or unacceptable) based on centration, movement and other fitting characteristics.
 
An unacceptable fit is deemed by one of the following criteria:
 
 • limbal exposure at primary gaze or with extreme eye movement; • edge lift; • excessive movement in primary and up gaze; or • insufficient movement in all three of the following conditions: primary gaze, 	[REDACTED]

		
up gaze, and Josephson push up.
 
If either lens is deemed unacceptable, the subject will be discontinued from the study. Remove the lenses, perform a slit-lamp evaluation, and complete the Final Evaluation form.
	
4.14	PRO Post-Fit Questionnaire	
The subject will evaluate the vision characteristics, comfort characteristics, handling characteristics, and visual symptoms of the study lenses using the PRO questionnaire.
	
4.15	Distance and Near Exit Visual Acuity	
Distance and near Snellen visual acuity will be measured for each eye with the study contact lenses in place.
 
For near measures use the ETDRS 2000 Series Chart 1 or 2. The acuity will be recorded to the nearest letter OD, OS and OU.
 
Note: The distance visual acuity must be at least 20/30 OU for the lenses to be dispensed.
	████████
4.16	Dispensing Criteria	
The lenses will be dispensed for 12 ± 2 days.
 
 • Distance Snellen acuity equal to or better than 20/30 OU • Subject must indicate that the vision is acceptable. • Subject must indicate that the comfort of the lenses is acceptable. • Lenses must have an acceptable general lens fit. 	
4.17	Patient Instructions	
Instruct the Subject the following:
 
 • The lenses will be worn on a daily wear basis. • OPTI-FREE® Replenish® solution will be used in a rub regime to disinfect and store the lenses each night in the lens case provided. • If determined necessary by the Investigator sterile non-preserved rewetting drops may be dispensed to be used as needed for dryness. • Subjects will be instructed to wear lenses 	

		
for a minimum of 6 hours a day, every day during the study.
 
 • Subjects will be instructed to wear their glasses when not wearing the study lenses. • Subjects will be instructed to bring their habitual contacts or spectacles to the next visit. 
Note: In the event a lens is lost or damaged, the subject will return to the investigator site for replacement. As much as reasonably possible, a damaged lens should be returned to the investigational site and then returned to the Sponsor. If lens damage is present, complete the Product Quality Complaint Form. The lens will be stored in labeled vial with sterile saline and returned to the Sponsor.
	
4.18	Schedule Follow-up	
The subject will be scheduled to return for their follow-up appointment in 12±2 day.
 
Note: To count the follow-up visit as a day of wear the Subject must have worn the study lenses for 6 hours prior to the visit.
	

VISIT 5

The subjects must present to Visit 5 wearing the study lenses. To be counted as a day of wear the lenses need to have been worn for at least six (6) hours prior to the visit.

Visit 5: Treatment 2 Follow-up 1		
Step	Procedure	Details
5.1	Adverse Events and Concomitant Medications Review	
Review the subject's concomitant medications and record any changes from the previous study visit.
 
Record any adverse events or medical history changes from the previous study visit.

5.2	Wear Time	
Record the hours the subject has worn the study lenses and the comfortable wear time on the day of follow-up.

5.3	Compliance	
Record the subject's compliance with wearing the study lenses.
 
Note: Subjects must have worn lenses for at least 6 hours per day To be counted as a day of wear at this visit the Subject must have worn the study lenses for 6

		hours prior to the visit.	
5.4	PRO and CLDEQ-8 Questionnaires	The subject will evaluate the vision characteristics, comfort characteristics, handling characteristics, and visual symptoms of the study lenses using the PRO questionnaire.	
5.5	Ocular Symptoms	Subjects will respond to a verbal open-ended symptoms questionnaire	[REDACTED]
5.6	Subjective Acceptance	Record whether the subjects distance and near vision with the lenses is acceptable.	
5.7	Distance and Near Entrance Visual Acuity	
Distance and near Snellen visual acuity will be measured for each eye with the study contact lenses in place.
 
For near measures use the ETDRS 2000 Series Chart 1 or 2. The acuity will be recorded to the nearest letter OD, OS and OU.
	[REDACTED]
5.8	Visual Performance Distance (3M) Intermediate (64 cm) Near (40 cm)	
Visual performance will be recorded OD, OS, and OU for the following:
 
Distance, Bright Illuminance High and Low Contrast ETDRS Charts 3M- HC#1, HC#2, HC#3 and LC#1, LC#2, LC#3
 
Near, Bright Illuminance Reduced Guillon-Poling Charts Intermediate (64 cm) High Contrast and Low Contrast Near (40 cm) High Contrast and Low Contrast
 
Distance, Dim Illuminance (with Distance goggles) High Contrast ETDRS Charts 3M-HC#4, HC#5, HC#6
 
Near, Dim Illuminance (with Near goggles) Reduced Guillon-Poling charts High Contrast Intermediate (64 cm) and Near (40 cm).
 
Note:
 
 • The room illuminance must be between 7.3 and 7.9 EV (394-597 lux). • Distance, HC-1 Chart luminance Acceptable Range 10.5-10.7 EV (181-208 cd/m²). • Guillon-Poling, Near Chart 	[REDACTED] [REDACTED] [REDACTED]

		
Luminance Acceptable Range 10.8-11.1 EV (223-274 cd/m²).
 
 • Do not use the Mesopic filter for Dim luminance (Dim luminance will be simulated by using the goggles) 	
5.9	Binocular Distance Over-refraction and Distance Visual Acuity	
Perform a binocular over-refraction and record the OD and OS results and distance visual acuity.
 
Note: No lens changes are allowed based on the over-refraction.
	Appendix D
5.10	Lens Fit Assessment:	
Evaluate and grade lens centration, primary gaze movement, upgaze movement and tightness (push-up test).
 
The subject should not proceed to wear the lenses if any of the following is observed:
 
 • presence of limbal exposure (appearance of clear cornea) in any gaze • presence of edge lift • presence of unacceptable movement (excessive or insufficient) in all three movement categories (primary gaze, upgaze, and push-up). 
If either lens is deemed unacceptable, the subject will be discontinued from the study. Remove the lenses, perform a slit-lamp evaluation, and complete the Final Evaluation form.
	
5.11	Lens Removal	
Have the subject remove the study lenses and store in saline in a labeled glass vial.
 
Note: Lenses do not need to be stored in a refrigerator.
	
5.12	Biomicroscopy	
Perform biomicroscopy OD and OS. Slit Lamp Classification Scales will be used to grade the findings.
 
For the conjunctival redness [REDACTED] 0.5 unit increments will be used in the grading.
 
Corneal Staining Assessment [REDACTED] will be graded in 1.0 increments.
 
If the clearance of the fluorescein needs to be expedited, preservative-free rewetting drops or saline may be instilled.
	[REDACTED] [REDACTED] [REDACTED]

FINAL EVALUATION

The final evaluation will ordinarily take place immediately following the last scheduled follow-up visit per the study protocol. It may also take place at any point the subject discontinues the study or is terminated from the study.

Final Evaluation		
Step	Procedure	Details
F.1	Distance Subjective Sphero-cylindrical Refraction and Distance Exit Visual Acuity	An optimal, binocular balanced distance sphero-cylindrical refraction will be performed. Record the refraction and distance visual acuity to the nearest letter.
F.2	Subject Disposition	Indicate if the subject completed the study successfully. If subject discontinued from the study indicate the reason.

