2.2. Endpoints

The study endpoints will be the subjective CLUE Vision scores and logMAR visual acuity. Additional endpoints will be a summary of lenses needed to fit (optimize) the subject, CLUE comfort/handling scores, the lens fit and ocular physiological responses.

Primary Endpoint

- CLUE vision scores

Secondary Endpoint

- logMAR visual acuity

Other Observations

- Lens fit
- Corneal staining
- Ocular redness (bulbar and limbal)
- Summary of lenses needed to fit (optimize) the subject
- CLUE comfort/handling scores
- PRO individual questions

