8. SUBJECTS COMPLETION/WITHDRAWAL

8.1. Completion Criteria

Subjects are considered to have completed the study if they:

- provided informed consent
- they are eligible
- completed all study visits

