8.2. Withdrawal/Discontinuation from the Study

A subject will be withdrawn from the study for any of the following reasons:

- Subject death during the study period
- Subject withdrawal of consent
- Subject not compliant to protocol
- Subject lost to follow-up
- Subject no longer meets eligibility criteria (e.g. the subject becomes pregnant)
- Subject develops significant or serious adverse events causing discontinuation of study lens wear
- Subjects who have experienced a Corneal Infiltrative Event (CIE)
- Investigator's clinical judgment regarding the subject safety reasons (that it is in the best interest of the subject to stop treatment)
- Subject missed two consecutive study visits
- Subject not compliant with study lens wear schedule

- Subject not successfully dispensed due to lack of efficacy and safety including poor vision, poor comfort or unacceptable fit

For discontinued subjects, the Investigator will:

- Complete the current visit (scheduled or unscheduled)
- Complete the Final Evaluation, indicating the reason that the subject was discontinued from the study
- Record the spherocylindrical refraction with best corrected distance visual acuity
- Collect used test article(s) (worn or brought to the visit) from the subject and discard them, unless otherwise stated in Section 6.7
- Collect all unused test article(s) from the subject

An additional subject may be enrolled if a subject discontinues from the study prematurely.

In cases where a subject is lost to follow-up, every possible effort must be made to contact the subject and determine the reason for discontinuation/withdrawal. The measures taken to follow up must be documented including two written attempts and a certified letter (or equivalent) as the final attempt.

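### Steps 3.10 and 5.10 discontinue subjects for poor lens fit at end-of-period visits, when no further wear follows; a Visit 3 failure loses valid period-1 data

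*Combined protocol and SAP*

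**What the plan says.** Section 7.2, step 3.10 (Visit 3) introduces the fit criteria with "The subject should not proceed to wear the lenses if any of the following is observed": limbal exposure, edge lift, or unacceptable movement in all three movement categories. It then states "If either lens is deemed unacceptable, the subject will be discontinued from the study" and sends the subject to the Final Evaluation. Step 5.10 (Visit 5) is the same, and both match steps 1.27 and 2.9 at the fitting and optimization visits. The step after 3.10 and 5.10 reads, for every subject, "Have the subject remove the study lenses and store in saline in a labeled glass vial".

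Other sections bear on what follows:

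- Section 8.1 defines completion by consent, eligibility and having "completed all study visits". It has no fit condition.
- Section 8.2 mentions fit in one withdrawal reason only: "Subject not successfully dispensed due to lack of efficacy and safety including poor vision, poor comfort or unacceptable fit". It also has discontinued subjects finish the current visit.
- Step F.2 makes the site record one disposition: "Indicate if the subject completed the study successfully".
- Section 2.2 names "the lens fit and ocular physiological responses" among the additional endpoints.
- Section 14.1 runs all analyses on the Per-Protocol population. Section 14.3 limits that population to subjects who successfully completed all visits without substantial deviation, as judged by a cohort review committee. An ITT population is defined, but no analysis is assigned to it.

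**The concern.** The rule makes sense where wear follows the check. At the end of a wearing period it does not: there is no further wear of that pair to prevent. The only effect of discontinuing at Visit 3 is to stop the subject from entering period 2, and under sections 14.1 and 14.3 that also removes the period-1 scores already collected.

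The removal depends on a post-randomisation response to the assigned lens. By construction, the Per-Protocol set would contain no unacceptable Visit 3 fit for either lens. If Test failed more often and failing subjects scored lower, dropping them would favour a finding of non-inferiority; if Control did, it would work against it.

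At Visit 5 the two-period data are complete, but the site must record a disposition on which steps 5.10 and 8.1 disagree. Nothing in the plan says which label decides Per-Protocol membership, so the committee is left to settle it.

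**Working it through.** **Order of events**

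| | Visit 3 | Visit 5 |
|---|---|---|
| CLUE | 3.4 | 5.4 |
| logMAR | 3.8 | 5.8 |
| Fit check and discontinuation | 3.10 | 5.10 |
| Lenses removed | 3.11 | 5.11 |
| Biomicroscopy | 3.12 | 5.12 |
| What follows | Washout in habitual correction (3.14), then Visit 4 | Final Evaluation |

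No study lens is dispensed at either visit, so the fit reason in section 8.2 does not apply.

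**Consequence at each visit.** Visit 3 failure: discontinued, Visits 4 and 5 missed, section 8.1 not met, outside the Per-Protocol set. Visit 5 failure: discontinued under 5.10, completed under 8.1, Per-Protocol status undetermined.

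**Size of a shift in the CLUE comparison.** The plan gives no figure on this point, neither a fit-failure rate nor a CLUE deficit for a poor fit, so the inputs below are assumptions. Take 50 completers, 25 per sequence, with the treatment estimate equal to the average of the two sequence means of Test minus Control. Suppose one subject fails at Visit 3 and scores d points lower on that lens, with no other lens difference:

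- Pair kept: that sequence mean moves by d/25, so the estimate moves by (d/25)/2 = d/50.
- Pair dropped: the estimate is 0.
- Shift from dropping: d/50, which is 10/50 = 0.2 points for d = 10 and 20/50 = 0.4 points for d = 20. It is positive if the failing lens is Test and negative if it is Control.

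In terms of failure rates fT and fC and deficit g, the shift from dropping Visit 3 failures is (fT − fC) × g / 2:

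| fT | fC | g | Shift (points) |
|---|---|---|---|
| equal | equal | any | 0 |
| 5% | 1% | 10 | 0.2 |
| 10% | 2% | 10 | 0.4 |
| 10% | 0% | 20 | 1.0 |

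A simulation of the third row gave −0.77 with all pairs kept and −0.38 with Visit 3 failures dropped, a shift of 0.39, in agreement. The margin is 5 points (section 2.3). All these figures assume the failing subjects would otherwise have completed period 2. No figure is given for Visit 5, because exclusion there depends on the committee.

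**Precision.** The 95% half-width is proportional to t(n1+n2−2) × √(1/n1 + 1/n2). Relative to 25 and 25, the ratio is 1.011 for 25 and 24, 1.033 for 24 and 23, and 1.035 for 25 and 22. Losing 1 to 3 subjects therefore widens the interval by 1.1% to 3.5%. Replacement, allowed by sections 5.2 and 8.2, removes this loss.

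**Whether section 14.9 covers it.** Multiple imputation is triggered by dropout above 15%.

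- 60 enrolled, 50 completers: 10/60 = 16.7%, runs.
- 60 enrolled, 51 completers: 9/60 = 15.0%, does not run.
- 59 enrolled, 50 completers: 9/59 = 15.3%, runs.
- 58 enrolled, 50 completers: 8/58 = 13.8%, does not run.

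It runs at the planned numbers but with little to spare, and section 14.9 does not name its analysis set.

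**The case against.** The strongest case is that stopping at Visit 3 changes little. The second lens has the same nominal base curve, diameter and centre thickness (Table 1), is given in the power dispensed at Visit 2, and is not optimized. Every pattern that fails 3.10 also fails 4.13, and 4.13 is stricter on excessive movement (primary and up gaze suffice). If the fit is unchanged, the subject is stopped at Visit 4 and leaves the Per-Protocol set anyway. This limits the benefit to subjects who pass 4.13 and complete Visit 5. It does not make the benefit nil: such a subject passed step 1.27 with fresh lenses of the same geometry, and at Visit 4 receives a fresh pair from the other curing process.

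Second, step 3.10 itself discards nothing; the loss comes from the Per-Protocol rules in 14.1 and 14.3, and any dropout after Visit 3 loses data in the same way. That is correct: the two act together. Here, though, the protocol itself causes the dropout.

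Third, steps 1.27, 2.9 and 4.13 also exclude on fit. They do, but there wear follows, which justifies the rule.

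Fourth, nothing is hidden, since the Safety Population summaries would still show the failures, and no numerical effect is shown at Visit 5. Both points stand.

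**Conclusion.** The concern holds. A rule written for visits at which lenses are dispensed has been carried to two visits where it serves no purpose for the pair being checked. At Visit 3 it causes an avoidable exclusion from the only population assigned to the analyses. At Visit 5 it contradicts section 8.1.

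The effect on CLUE or logMAR is of unknown size and direction and is probably small. The lenses share nominal geometry, fit has already been checked at 1.27 and 2.9, and bias needs unequal failure between lenses. The illustrated 0.2 to 0.4 points is 4% to 8% of the CLUE margin; even the extreme assumed case reaches only 1.0 point. The case for changing the text rests on its being cheap and removing a contradiction, more than on the likely bias.

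**What to change.** - **Step 5.10:** delete the discontinuation sentence, record the fit grade, and code the subject as completed under section 8.1.
- **Step 3.10:** replace the discontinuation sentence, and the instruction after it to complete the Final Evaluation form, with: *Record the fit grade. An unacceptable grade at this visit does not by itself discontinue the subject; fit of the second lens is decided at step 4.13.* Removal and biomicroscopy already follow at 3.11 and 3.12.
- **Section 14.3:** add: *A Visit 3 or Visit 5 fit grade does not by itself exclude a subject from the Per-Protocol set.*

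Withdrawal under section 8.2 on the investigator's "clinical judgment regarding the subject safety reasons" is unchanged. Biomicroscopy (4.5), the continuance decision (4.6) and the fit check (4.13) still come before any wear of the second lens.

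The cost is wording in two steps and one sentence in the statistical section, with no new procedure. A few subjects may attend Visit 4 only to be stopped at 4.13; they would leave the Per-Protocol set like any other dropout.
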